5.5 Secondary analyses

5.5.1. We will calculate summary statistics for the age and number of women not eligible for MRI, eligible and invited for MRI, women declined MRI and women undergoing MRI; including reason for non-participation (contraindication, patient choice, no response): for the entire study period, and how it changes over time.

5.5.2. We will calculate summary statistics and graphically show the distribution of AI scores for: i) Joint model, ii) AI risk score, iii) AI masking score, iv) AI CAD score(s). We will subgroup these analysis by age group at the time of initial screening: 40-49, 50-59, 60-69 and 70-74 years. We will subgroup these analysis by participation category (eligible vs. not eligible for MRI, invited vs. not invited for MRI, eligible women undergoing vs. not undergoing MRI, declined MRI (by reason)).

5.5.3. a) For women invited to MRI, we will calculate the number and proportion of breast cancer diagnosed by screening MRI, and perform logistic regression analysis to examine associations with AI scores (joint and component scores), age of the woman, by responses in the study persion questionnaire (see section 4.2.5), by BI-RADS scores of amount of fibgroglandular tissue and background parenchymal enhancement. Similar analysis will be carried out for all cancers diagnosed during the study time. We will repeat the analyses for women actually undergoing MRI.

b) We will perform similar analyses as above for all women undergoing mammography only, but by necessity exclude parameters that are not collected for those women.

For all cancers diagnosed, the tumor characteristics listed in section 4.2.3 will be reported, overall and divided by women eligible or not eligible for MRI, as well as for women invited vs. not invited to MRI, eligible women undergoing vs. not undergoing MRI.

5.5.4. We will calculate summary statistics for the radiological process measures described in 4.2.4.

5.5.5. We will calculate summary statistics for each of the questionnaire responses described in 4.2.5.

5.7 Sample size

The sample size calculation relates to the primary analysis after women have undergone the baseline mammogram. We have estimated that the study would have a at least 90% power in detection of a statistically significant (p<0.05) difference in the absolute incidence of the primary endpoint of significantly delayed cancer (defined in 4.1), under the following assumptions:

- 50% of the women invited will agree to participate (not relevant)
- 84% of the significantly delayed cancers are averted by undergoing MRI (based on DENSE trial)

- 80% of the women will participate in the subsequent screening (around two years after the initial screening)
- 28.6 (approximately twice as many cancers detected as we assumed before study start) per 1000 women having a significantly delayed detection in the population selected by the AI tool
- The randomization rate will be around 1:1 for MRI vs. no-MRI (standard of care)

5.8 Adjustment for multiplicity

We will not perform any correction for multiple comparisons. Each analysis will be presented with unadjusted 95% confidence interval.

5.9 Handling of missing data

Endpoints

Our primary approach is of intention-to-treat-type (defined by which arm they are randomized to, MRI or not MRI); for any examination where the I process failed, study inclusion is not possible. In addition, we will perform a per-protocol analysis (defined by whether they underwent MRI or not).

Patient characteristics

Since data collection is performed through the electronic medical record, missing data is expected to be minimal. For analyses where patient characteristics are used (e.g., analyzing the interaction between a patient characteristics and study outcomes), we will exclude patients with missing data. As a sensitivity analysis, we will impute the missing data using the mean or median, whichever is appropriate.

5.10 Analysis of non-invitations of eligible women

Interim analysis performed in March, 2023, showed that 423 women had an AI Joint Score above the threshold but had not been invited to randomization due to technical errors. These women were erroneously excluded from randomization and therefore never had the chance to be selected for MRI. We have no reason to believe that the technical error was related to the endpoints of this study, but we nevertheless intend to perform analysis to estimate whether this exclusion corresponds to a random sample by comparing the age and mammographic density distribution between the invited eligible women and the non-invited eligible women. If we determine that it was not a random sample, we will, in sensitivity analysis, employ randomization and imputation of the clinical outcome for women randomized to MRI.

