4.2 Secondary endpoints

To the extent that a secondary outcome measure does not overlap with the primary outcome, it may be included in interim reporting.

4.2.1. Number and age of women eligible and not eligible for MRI, women invited, women declined and women accepted to participate; including reason for non-participation (contraindication, patient choice, no response).

4.2.2. Distribution of AI scores for: i) Joint model, ii) AI risk score, iii) AI masking score, iv) AI CAD score(s).

4.2.3. a) Breast cancer diagnosed by screening MRI.

b) All breast cancers diagnosed during the study time including the initial screening, including mode of detection (MRI, mammographic detection, clinical detection including time since screening) for all women for whom AI scores were calculated (above and below threshold)

For all cancers in the outcome measures, the following tumor characteristics will be reported:

a) Invasiveness (in situ or invasive; micro-invasive counted as in situ)

b) Histology (ductal, lobular, mucinous, tubular, other)

c) Lymph node status (0, 1-3, or more than 4 lymph node metastases)

d) Tumor size (in mm) – in situ and invasive component separately measured by pathologist

e) Ki-67 percent. With a 20% binary cut-off, and an ex 14% cut-off level

d) Molecular subtype (Luminal A-like defined as estrogen and/or progesterone receptor positive and HER2 negative and KI-67 <14%, Luminal B-like defined as estrogen and/or progesterone receptor positive and HER2 positive/negative and KI-67 >=14%, HER2-positive defined as estrogen and progesterone receptor negative and HER2 positive, and Triple negative defined as estrogen and progesterone receptor and HER2 negative)

4.2.4. Radiological process measures: distribution of BI-RADS scores (amount of fibroglandular tissue, background parenchymal enhancement, and any lesion); number and outcome of second look ultrasound, biopsies, short-term MRI follow-up. We will report operational characteristics of the screening MRI (cancer detection rate, recall rate, positive predictive value for 2nd look ultrasound decision and for biopsy decision).

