5.1 Populations

The study population consists of all consecutive women attending regular screening mammography at Karolinska University Hospital in Stockholm having a normal assessment (i.e., not being recalled for further assessment by the consensus discussion). The prior data for each woman consists of: mammographic images, date of examination, age at examination, assessment by first radiologist, assessment by second radiologist, decision by consensus discussion (if any), AI scores from the three component models and a summary score, pathology-verified cancer diagnosis (if any) including key cancer characteristics (listed in section 4.2).

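### SAP 5.10 judges whether the 423 uninvited women are a random sample from age and density alone, leaving out the AI scores and examination date held for every woman

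*Combined protocol and SAP*

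**What the plan says.** SAP 5.10 states that "423 women had an AI Joint Score above the threshold but had not been invited to randomization due to technical errors", and adds: "These women were erroneously excluded from randomization and therefore never had the chance to be selected for MRI". The authors see no reason to link the fault to the endpoints but plan to check, by "comparing the age and mammographic density distribution between the invited eligible women and the non-invited eligible women". No other variable and no criterion is named. The result works as a gate: "If we determine that it was not a random sample, we will, in sensitivity analysis, employ randomization and imputation of the clinical outcome" for women allocated to MRI.

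The SAP holds more than this. Section 5.1 lists for each woman the "AI scores from the three component models and a summary score", and also the "date of examination, age at examination". Section 4.3 (fourth exploratory objective) names AI scores beside age and density as potential predictors of cancer incidence and detection. Section 5.5.2 plans to describe the distributions of all AI scores: "We will subgroup these analysis by participation category (eligible vs. not eligible for MRI, invited vs. not invited for MRI". Section 5.5.1 describes participation over time, and 5.5.3 describes tumour characteristics by invitation status. None of these outputs is tied to the decision in 5.10.

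**The concern.** The AI tool was built to find women likely to have a delayed diagnosis, so its scores are the most direct baseline predictors of the primary endpoint that the trial has. A check for an endpoint-related loss that omits them can miss what it is looking for. The 423 women were scored, so the fault acted after scoring. Nothing in the documents says whether it was spread evenly over the study or concentrated in some weeks, and age and density carry no information on that.

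Examination date has a second use. The protocol (Study Type) lets the numbers allocated to each group follow MRI capacity over time, so any later simulated randomisation of the 423 depends on when they were screened.

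The masking score also has a second use. Section 5.3 sets a cut-off on both the Joint Score and the Masking Score, while 5.10 describes the 423 by the Joint Score only. A comparison of masking scores would show whether they met both.

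If the check wrongly finds a random sample, the sensitivity analysis is not run. Readers then have no signal that the randomised women, and the absolute event rate seen in them, may not stand for all women whom the tool selects.

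**Working it through.** The plan gives no figure for this check, so there is none to reproduce. The point rests on the choice of variables; the numbers below only illustrate it.

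**Inputs.** Missed women: 423 (SAP 5.10). Primary-endpoint rate: about 14 per 1000 (SAP 5.3) or 28.6 per 1000 (SAP 5.7). The documents do not give the number of invited women, so I assume m = 1,000 to 3,000. The 423 are then 423/(423 + m) = 30% to 12% of all above-threshold women.

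**Variables side by side.**

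| Variable | Available or planned | Decides in 5.10? |
|---|---|---|
| Age | 5.1 | yes |
| Mammographic density | 4.3 | yes |
| Joint and component AI scores | 5.1, described in 5.5.2 | no |
| Examination date | 5.1, time trends in 5.5.1 | no |

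**Precision of a comparison.** The SE of a standardised difference is sqrt(1/423 + 1/m).
- m = 1,000: SE 0.058, 95% half-width 0.11.
- m = 3,000: SE 0.052, 95% half-width 0.10.

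**What density alone would see.** Assume the loss is tied to the cancer-signs score with a shift of 0.5 SD, and that this score correlates with density by r. The density shift is 0.5 × r. Two-sided 5% power with m = 3,000:
- r = 0: shift 0, 5% (the false-positive rate).
- r = 0.1: shift 0.05, 16%.
- r = 0.2: shift 0.10, 49% (41% to 46% for m = 1,000 to 2,000).
- r = 0.3: shift 0.15, 82% (73% for m = 1,000).

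The score compared directly: 0.5/0.052 = 9.6 standard errors, power about 100%.

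**What age and density together would see.** If the score is independent of both, the chance that at least one of two 5% tests flags is 1 − 0.95² = 9.75%, whatever the size of the loss. A simulation with 423 missed, 1,500 invited and a score shift of 0.4 SD agrees: age or density flags in 9% to 10% of runs, the score in about 100%.

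Selection on the Joint Score makes age and the components correlated, which helps the planned check. I assumed normal components with pairwise correlation 0 to 0.3, a masking–density correlation of 0.5 to 0.7, ages uniform on 40 to 74, selection of the top 8% with masking above the median, and a 0.5 SD shift (423 versus 3,000). Power is then about 29% to 46% for age and 10% to 35% for density.

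**What outcomes would add.** Expected events in the 423 if the loss is random: 423 × 0.014 = 5.9 and 423 × 0.0286 = 12.1. The 95% half-width of that proportion, 1.96 × sqrt(p(1 − p)/423), is 1.1 to 1.6 percentage points. Against an assumed 500 to 1,000 women without MRI, power to detect a doubled rate is 33% to 45% at 14 per 1000 and 58% to 72% at 28.6 per 1000.

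**The case against.** The strongest reply is that the SAP already covers most of this. Section 5.5.2 gives score distributions by invitation status, 5.5.1 gives time trends, and 5.5.3 gives tumour characteristics. That is correct, and a reader who inferred that the plan ignores the scores would be wrong. What remains is narrower: these outputs do not feed the 5.10 judgement, and the split by invitation is not clearly limited to women above the threshold. Most uninvited women are below it, so an unrestricted comparison would mainly show the selection rule.

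Three stronger readings also fail.
- A reader might infer that the loss biases the treatment effect. Section 5.10 places it before randomisation, so the contrast between arms is unaffected.
- A reader might infer that the endpoint was already available for the 423 when the check was written. With a start on April 1, 2021 and 27 months of follow-up, the earliest complete follow-up is July 2023, after the March 2023 revision. Outcomes come from later registry and record linkage.
- A reader might infer that the check decides what the trial reports as representative. The only stated consequence is the sensitivity analysis.

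It is also fair that no passage suggests a score-dependent or time-clustered fault, that the shifts and correlations above are assumptions, and that age and density are partial proxies because age multiplies the Joint Score and density is plausibly linked to masking. Radiologist assessments would add little, since only women who were not recalled are eligible.

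**Conclusion.** The concern holds in this limited form: the gate in 5.10 rests on two partial proxies although better variables are held for every woman. Under the assumptions shown, density or age taken singly would detect a substantial score-linked loss with power from about 5% to 50% in most scenarios, and density would reach 73% to 82% if its correlation with the score were 0.3. Direct comparison of the score would detect the same loss almost surely. Clustering in time can be seen only if date is compared.

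The primary estimate, its confidence interval and the comparison of arms are not affected. The consequence is limited to representativeness, the absolute event rate and the decision on the sensitivity analysis. The conclusion about the choice of variables does not depend on the assumed number of invited women; the power figures do, though only modestly over 1,000 to 3,000.

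**What to change.** Amend SAP 5.10 as follows.

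1. Among above-threshold women only, compare invited and non-invited women on the AI Joint Score, the component scores (risk, masking, cancer signs) and examination month, as well as age and density.
2. Report standardised differences with 95% CIs, and base the random-sample judgement on all of these. Say in advance what size of difference would count. With 423 missed women the half-width is about 0.10 to 0.11, so a limit well below that cannot be resolved.
3. When linked outcomes become available, show the primary-endpoint proportion in the 423 with a CI, descriptively. It should not decide the question.

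The cost is SAP wording and one table from baseline data already held, with the outcome line added after linkage. No new data collection is needed, and the primary analysis does not change.
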